- 6) Investigators will fill out the case report form for each patient following the 24-week observation period without delay, and provide it to a medical representative. When a patient discontinues treatment during the observation period, the investigator will follow up the patient until the end of the 24-week observation period, fill out the case report form for him/her at the end of the observation period, and provide it to a medical representative.
- 7) The sponsor will confirm the contents of the registration and case report forms, and perform reinvestigation whenever necessary.
- 8) Medical representatives will also visit investigators once every week or every other week, in principle, to monitor for the occurrence of adverse events, provide proper use information, and determine the progress of patient registration.
- 9) Following the 24-week observation period, the investigator will evaluate each patient for malignancy annually for 2 years after the initiation of Humira treatment using a separate follow-up investigation form. When the occurrence of malignancy is found in a patient, the investigator will perform detailed investigation of him/her. Investigators will be instructed to report the occurrence of malignancy to the sponsor without delay when they are found, regardless of the timing of follow-up investigation.
- 10) Adverse Event Reporting  
In the event of a serious adverse event, and additionally, any non-serious events of malignancy in patients 30 years of age and younger, whether related to adalimumab or not, if applicable - the physician will notify the AbbVie contact person (Medical Representative in Japan) within 24 hours of the physician becoming aware of the event.

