## 2. Definition of terms and abbreviations

The terms and abbreviations used in this statistical analysis plan are defined as follows.

Terms and abbreviations	Definition
Adverse events	An adverse event refers to any unfavorable and unintended sign (including an abnormal laboratory finding), symptom or disease associated with the use of a drug, whether or not considered related to the drug.
Adverse events during the safety analysis period	Adverse events that occurred during the period up to the start date of Humira treatment + 196 days.
Adverse events outside the safety analysis period	Adverse events that occurred prior to the start date of Humira treatment or after the start date of Humira treatment + 196 days.
Adverse reactions	Of adverse events, events for which causal relationship with Humira cannot be ruled out are defined as adverse reactions.
Adverse reactions during the safety analysis period	Of adverse events during safety analysis period, events for which a causal relationship with Humira cannot be ruled out are defined as adverse reactions during safety analysis period.
Adverse reactions outside the safety analysis period	Of adverse events outside safety analysis period, events for which a causal relationship with Humira cannot be ruled out are defined as adverse reactions outside the safety analysis period.
Basic statistics	Basic statistics include sample size, mean value, standard deviation, minimum value, median value, maximum value, first quartile and third quartile.
MedDRA/J	Medical Dictionary for Regulatory Activities/Japanese edition
SOC	MedDRA/J System Organ Class
PT	MedDRA/J Preferred Term
CDAI	Clinical Disease Activity Index
CRP	C-Reactive Protein
DAS	Disease Activity Score
DMARDs	Disease Modifying Antirheumatic Drugs
EULAR	European League Against Rheumatism
ESR	Erythrocyte Sedimentation Rate
JIA	Juvenile idiopathic arthritis
MTX	Methotrexate
NSAIDs	Non-Steroidal Anti-Inflammatory Drugs
SDAI	Simplified Disease Activity Index
VAS	Visual Analog Scale

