	
1), it should be 1.
 
If “>=1” (1 or greater), the number should be rounded down to the nearest integer.
 
(5) The total number of doses should be the sum of (4) for each patient.
 
 
• Total dose
 
 
(1) If the dose of Humira is “other”, it should be obtained from “External file for provision of analysis”.
 
(2) Doses should be calculated for each data on treatment status.
 
Dose = number of doses x dose
 
(3) The total dose should be the sum of (2) for each patient.
 
 
• Mean dose
 
 
Mean dose = total dose / total number of doses

Discontinued patients	When the end date of Humira treatment is less than 24 weeks (168 days) after the start date of Humira treatment, the patient should be handled as a discontinued patient.
Reason for discontinuation	In the case of discontinued patients, data should be derived from “Reason for discontinuation” under “3. Discontinuation of treatment” of the CRF or “External file for provision of analysis”. If any data have not been provided, it should be handled as “unknown/unspecified”. “Onset of an adverse event” should apply only when “Onset of an adverse event” is selected and an adverse event during the safety analysis period has occurred.
Date of discontinuation of treatment	In the case of discontinued patients, the end date of Humira treatment should be the date of discontinuation. Where the start date of Humira treatment + 168 days > the end date of Humira treatment, the end date of Humira treatment should be the date of discontinuation.
Patients switched to other biological products	Patients falling under discontinued patients, for whom “Switching to another drug” is selected for “Treatment status after discontinuation” under “3. Discontinuation of treatment” of the CRF and whose “Drug name” falls under codes of biological products listed in “Drug code list 20171012.xlsx”.
Reason for switching	In the case of patients switched to other biological products, data should be derived from “Reason for discontinuation” under “3. Discontinuation of treatment” of the CRF or “External file for provision of analysis”. If any data have not been provided, it should be handled as “unknown/unspecified”. “Onset of an adverse event” should apply only when “Onset of an adverse event” is selected and an adverse event during the safety analysis period has occurred.

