Timing of onset of adverse events	
With the start date of treatment as Day 1
 
Adverse events that occurred after the start of treatment and within 4 weeks of treatment (Days 1 to 28)
 
Adverse events that occurred after Week 4 of treatment and within 8 weeks of treatment (Days 29 to 56)
 
Adverse events that occurred after Week 8 of treatment and within 12 weeks of treatment (Days 57 to 84)
 
Adverse events that occurred after Week 12 of treatment and within 16 weeks of treatment (Days 85 to 112)
 
Adverse events that occurred after Week 16 of treatment and within 20 weeks of treatment (Days 113 to 140)
 
Adverse events that occurred after Week 20 of treatment and within 24 weeks of treatment (Days 141 to 168)
 
Occurrence of adverse events after the end of treatment: Adverse events that occurred at and after Week 24 of treatment (on and after Day 169)

Adverse events occurred during treatment	Adverse events that occurred after the start date of Humira treatment by the end date or the date of discontinuation of Humira treatment
Adverse events occurred after treatment	Adverse events that occurred after the end date or the date of discontinuation of Humira treatment by the start date of Humira treatment + 196 days
Serious adverse events	Adverse events whose seriousness set through the AE matching activities is “serious” are defined as serious adverse events.
Adverse reactions	
Adverse events whose causal relationship is other than “not related” based on company-determined data set through the AE matching activities are defined as adverse reactions.
 
Adverse reactions with the same case number should be counted as one event when the PT is the same.
 
Name of analytical dataset: A_AE_AL
 
Names of variables: AERELS, AESOCCD, AEPTCD

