Purpose of analysis: Involving adverse reactions during the safety analysis period, the number of patients and the number and percentage of patients who experienced adverse reactions will be calculated in accordance with “11. Data-layer separation” (age 1, age 2, age 3, sex, body weight, BMI, reason for use and type of disease, disease duration 2, complications, complication: liver disorder, complication: renal disorder, complication: cardiovascular disorder, complication: blood disorder, complication: respiratory disorder, complication: other, past medical history, history of allergy, Steinbrocker Staging System, Steinbrocker Functional Classification, administration method category, previous medications, status of previous medication: biological product, status of previous medication: MTX, status of previous medication: corticosteroid, status of previous medication: NSAIDs, status of previous medication: Other DMARDs, concomitant drugs, status of concomitant drug: MTX, status of MTX: details, status of concomitant drug: corticosteroid, status of concomitant drug: NSAIDs, status of concomitant drug: Other DMARDs).

For the incidence rates of adverse reactions, Fisher's exact test should be conducted when the background factor is a nominal scale and Mann-Whitney U test should be conducted when the background factor is an ordinal scale.

Notes: • Reason for use and type of disease may be redundantly aggregated. No test will be conducted for this item.

“Table 2.5.2 Incidence of adverse events in patients switched to other biological products”

Analysis object: Patients included in the safety analysis set

Purpose of analysis: Involving adverse events during the safety analysis period, the number of patients, the number and percentage of patients who experienced adverse events will be calculated on the basis of the number of patients switched to

other biological products and the breakdown of the reasons for switching (remission, subtherapeutic response, onset of adverse events, patient's request, no hospital visit [including hospital transfer], other).

Notes:

- The breakdown of the reasons for switching may be redundantly aggregated.
- “Onset of an adverse event” should apply only when “Onset of an adverse event” is selected and an adverse event during safety analysis period has occurred.

“Table 2.5.3 Incidence of adverse reactions to combination therapy for juvenile idiopathic arthritis”

Analysis object: Patients included in the safety analysis set

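### Table 2.5.2 pools switchers' adverse events during and after Humira, and its adverse-event-onset row carries no incidence information by construction

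*SAP*

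**What the plan says.** SAP 13.2, Table 2.5.2, covers patients who moved from Humira to another biologic, overall and by reason for switching: "Involving adverse events during the safety analysis period, the number of patients, the number and percentage of patients who experienced adverse events will be calculated". It counts adverse events of any cause. Tables 2.5.1, 2.5.3 and 2.5.4 count adverse reactions instead.

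The other parts sit elsewhere in the documents:

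- **Event window** (SAP 2): "Adverse events that occurred during the period up to the start date of Humira treatment + 196 days". It does not depend on when Humira stopped.
- **Switcher** (SAP 10.1): "Patients falling under discontinued patients, for whom “Switching to another drug” is selected", with the new drug coded as a biologic.
- **Discontinued patient** (SAP 10.1): "When the end date of Humira treatment is less than 24 weeks (168 days) after the start date of Humira treatment".
- **Follow-up after stopping** (protocol section 6): "the investigator will follow up the patient until the end of the 24-week observation period".
- **Adverse-event-onset row** (note to Table 2.5.2, and SAP 10.1 on the reason for switching): a patient counts here only if that reason was selected and "an adverse event during safety analysis period has occurred".
- **After-treatment phase** (SAP 10.2): "Adverse events that occurred after the end date or the date of discontinuation of Humira treatment by the start date of Humira treatment + 196 days". A matching during-treatment phase is defined beside it. Tables 2.16.1 and 2.16.2 use both phases; Table 2.5.2 uses neither.

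**The concern.** Two features of the table limit what it can tell a reader.

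First, every switcher stopped Humira inside the counting window and was followed afterwards. A single rate over the whole window cannot separate events that came before the end of Humira from those that came after. Because the table takes events of any cause, no causality filter removes events that arose later on a different product.

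Second, the condition for entering the adverse-event-onset row is the same condition that puts a patient in the numerator. The row's result is settled before any data are seen.

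The SAP says its results feed the report to the authorities and the reexamination file (SAP 3.1). What is at stake is how a descriptive safety table is read there. No test or primary result depends on it.

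**Working it through.** **The plan's own figure.** The documents give no number for Table 2.5.2. The only numerical target is the protocol's sample-size rationale, and it reproduces: 1 − 0.97^100 = 0.952, against 95% stated. It has no bearing on this point.

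**Step 1: every switcher has time after Humira in the window.** Let *d* be the number of days from Humira start to Humira end. For a discontinued patient *d* is at most 167. The window ends at +196, so the time after Humira is 196 − *d*, which is at least 196 − 167 = 29 days (29/196 = 15%).

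**Step 2: share of time after Humira.** The share is (196 − *d*)/196 of the SAP window. Protocol observation ends at 24 weeks, so the share of observed time is (168 − *d*)/168.

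| Humira end (*d*) | SAP window | Observed 168 days |
|---|---|---|
| 28 | 168/196 = 86% | 140/168 = 83% |
| 56 | 140/196 = 71% | 112/168 = 67% |
| 112 | 84/196 = 43% | 56/168 = 33% |

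**Step 3: what pooling could do to a rate.** The documents give no event rate, so this is an illustration only. Assume a constant rate λ per patient-year, equal before and after the end of Humira, and Humira ending at day 84. Counting both end days, the window is 197 days and the Humira phase 85. The proportion with at least one event is 1 − exp(−λ × days/365.25).

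| Assumed λ | Whole window | Humira phase only |
|---|---|---|
| 0.5 | 23.6% | 11.0% |
| 1 | 41.7% | 20.8% |
| 2 | 66.0% | 37.2% |
| 4 | 88.4% | 60.6% |

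**Step 4: the adverse-event-onset row.** Let A be the switchers with that reason selected and B the switchers with an event by +196 days. The row's members are A ∩ B. Its numerator is the members with an event by +196 days, (A ∩ B) ∩ B = A ∩ B. Numerator and row size are the same set in any data.

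**Step 5: which denominator.** Table 2.5.2 states none. There are three candidates:

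- The row itself, the natural reading: the percentage is 100%.
- All switchers, as Table 1.2 uses for its breakdown: the percentage repeats the Table 1.2 entry.
- The analysis set, the default in SAP 9.10: the percentage is the row count over the safety set.

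Under none of them does the row give an incidence.

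**Step 6: timing of the qualifying event.** B runs to +196 days and is not cut at the Humira end date. A patient with the reason selected, whose only recorded event came after Humira, still enters the row.

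**The case against.** The strongest reply is that the timing is available elsewhere. Table 4.2 lists each patient's event onset dates, causality, Humira start and end dates, and status after discontinuation. Table 4.3 gives the drug after switching. Table 2.16.1 splits events during and after treatment for discontinued patients, who include every switcher, and the protocol asks for no switching analysis. All of that is correct, so a claim that the outputs cannot show whether events preceded the end of Humira would fail. It does not repair the summary. Table 2.16.1 pools switchers with all other discontinued patients, and a listing leaves the reader to rebuild the split by hand.

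Other stronger readings are tempting, and the documents do not support them:

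- **The onset row's incidence before the switch is also fixed at 100%.** It is not. By Step 6, only the whole-window figure is predetermined. The during-treatment figure can vary, and it is the one that would test the stated reason.
- **The printed percentage must be 100%.** That needs the row as denominator, which the table does not state.
- **Events after Humira are events on the next biologic.** There may be a gap, and the SAP derives no start date for the new drug. Its concomitant-drug window closes at the Humira end date.
- **The table attributes later events to Humira.** Its title refers only to adverse events in patients who switched. Attribution rests on the adverse-reaction tables, which this one does not feed.

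**Conclusion.** The point holds in a limited form. Table 2.5.2 mixes events during Humira with events after it for every switcher, and its adverse-event-onset row carries no incidence information. Both follow from the SAP's definitions and need no assumption about the data.

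The size can be given only as time: 86%, 71% and 43% of the SAP window, or 83%, 67% and 33% of the observed 24 weeks, for a Humira end at day 28, 56 and 112. A reader might take these as shares of events, or of exposure to the next biologic. They are neither, and are at most an upper limit for the second. The rates in Step 3 rest on an assumed constant event rate. Capture between day 168 and day 196 may be incomplete, because protocol observation ends at 24 weeks.

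The number of switchers is not given, so no effect on an actual result can be stated. The table is descriptive and untested. The change is worth making because it is cheap and the present layout invites misreading.

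**What to change.** Amend Table 2.5.2 in the SAP:

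1. Report events in the two SAP 10.2 phases, during treatment and after treatment to +196 days, cut at the Humira end date. Note that a patient with events in both phases counts in each, so the two counts need not add to the total.
2. Keep both phases for every reason row, including adverse-event onset. For that row, either omit the whole-window percentage or define the row by the selected reason alone.
3. State that each percentage uses the number of switched patients in that row. SAP 9.10 requires a footnote wherever the denominator is not the analysis set.
4. Label the second phase as after Humira, not as on the next biologic.

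The cost is a wording change and one extra column group, using onset dates and Humira end dates that the listings already require. The drawback is sparse cells: six reasons by two phases, among an unknown number of switchers in a survey planned for 100 patients.

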#### “Table 2.8 Incidence of adverse reactions by age”

Analysis object: Patients included in the safety analysis set

Purpose of analysis: Adverse reactions during the safety analysis period will be aggregated in accordance with “11. Data-layer separation” (age 1) as shown below. The number of patients analyzed, the number and percentage of patients who experienced adverse reactions, the number of adverse reactions, the number of patients who experienced adverse reactions by type of adverse reaction (by SOC and PT) and their percentages against the patients analyzed will be calculated.

Number of patients who experienced adverse reactions: Number of patients who experienced adverse reactions.

Number of adverse reactions: Number of adverse reactions that occurred. When a single patient experienced multiple episodes of the same adverse reaction (PT), they should be counted as one event.

Types of adverse reactions: Should be calculated by SOC and by PT. Output data should be sorted in the order of international agreements and in the ascending PT code order. When a single patient experienced multiple episodes of the same adverse reaction (PT), they should be counted as one event.

Note: The version of MedDRA/J used should be provided.

#### “Table 2.9 Incidence of adverse reactions in patients who received an increased dose”

Analysis object: Patients included in the safety analysis set

Purpose of analysis: Adverse reactions during the safety analysis period will be aggregated in accordance with “11. Data-layer separation” (dosage and administration category) as shown below. The number of patients analyzed, the number and percentage of patients who experienced adverse reactions, the number of adverse reactions, the number of patients who experienced adverse reactions

by type of adverse reaction (by SOC and PT) and their percentages against the patients analyzed will be calculated.

Number of patients who experienced adverse reactions: Number of patients who experienced adverse reactions.

Number of adverse reactions: Number of adverse reactions that occurred. When a single patient experienced multiple episodes of the same adverse reaction (PT), they should be counted as one event.

Types of adverse reactions: Should be calculated by SOC and by PT. Output data should be sorted in the order of international agreements and in the ascending PT code order. When a single patient experienced multiple episodes of the same adverse reaction (PT), they should be counted as one event.

Note: The version of MedDRA/J used should be provided.

“Table 2.10 Incidence of adverse reactions in patients who self-administered Humira”

Analysis object: Patients included in the safety analysis set

Purpose of analysis: Adverse reactions during the safety analysis period will be aggregated in accordance with “11. Data-layer separation” (self-administration) as shown below. The number of patients analyzed, the number and percentage of patients who experienced adverse reactions, the number of adverse reactions, the number of patients who experienced adverse reactions by type of adverse reaction (by SOC and PT) and their percentages against the patients analyzed will be calculated.

Number of patients who experienced adverse reactions: Number of patients who experienced adverse reactions.

Number of adverse reactions: Number of adverse reactions that occurred. When a single patient experienced multiple episodes of the same adverse reaction (PT), they should be counted as one event.

Types of adverse reactions: Should be calculated by SOC and by PT. Output data should be sorted in the order of international agreements and in the ascending PT code order. When a single patient experienced multiple episodes of the same adverse reaction (PT), they should be counted as one event.

Note: The version of MedDRA/J used should be provided.

“Table 2.11 Incidence of adverse reactions by dose of MTX per body surface area”

Analysis object: Patients included in the safety analysis set

Purpose of analysis: Adverse reactions during the safety analysis period will be aggregated in accordance with “11. Data-layer separation” (status of concomitant drug: MTX, status of MTX: details) as shown below. The number of patients analyzed, the number and percentage of patients who experienced adverse reactions, the number of adverse reactions, the number of patients who experienced adverse reactions by type of adverse reaction (by SOC and PT) and their percentages against the patients analyzed will be calculated.

Number of patients who experienced adverse reactions: Number of patients who experienced adverse reactions.

Number of adverse reactions: Number of adverse reactions that occurred. When a single patient experienced multiple episodes of the same adverse reaction (PT), they should be counted as one event.

Types of adverse reactions: Should be calculated by SOC and by PT. Output data should be sorted in the order of international agreements and in the ascending PT code order. When a single patient experienced multiple episodes of the same adverse reaction (PT), they should be counted as one event.

Note: The version of MedDRA/J used should be provided.

“Table 2.12 Incidence of adverse reactions by history of treatment with biological products”

Analysis object: Patients included in the safety analysis set

Purpose of analysis: Adverse reactions during the safety analysis period will be aggregated in accordance with “11. Data-layer separation” (status of previous medication: biological products) as shown below. The number of patients analyzed, the number and percentage of patients who experienced adverse reactions, the number of adverse reactions, the number of patients who experienced adverse reactions by type of adverse reaction (by SOC and PT) and their percentages against the patients analyzed will be calculated.

Number of patients who experienced adverse reactions: Number of patients who experienced adverse reactions.

Number of adverse reactions: Number of adverse reactions that occurred. When a single patient experienced multiple episodes of the same adverse reaction (PT), they should be counted as one event.

Types of adverse reactions: Should be calculated by SOC and by PT. Output data should be sorted in the order of international agreements and in the ascending PT code order. When a single patient experienced multiple episodes of the same adverse reaction (PT), they should be counted as one event.

Note: The version of MedDRA/J used should be provided.

“Table 2.13 Incidence of adverse reactions in children and non-children”

Analysis object: Patients included in the safety analysis set

Purpose of analysis: Adverse reactions during the safety analysis period will be aggregated for children (aged <15 years) and non-children (aged ≥15 years) as shown below. The number of patients analyzed, the number and percentage of patients who experienced adverse reactions, the number of adverse reactions, the number of patients who experienced adverse reactions by type of adverse reaction (by SOC and PT) and their percentages against the patients analyzed will be calculated.

Number of patients who experienced adverse reactions: Number of patients who experienced adverse reactions.

Number of adverse reactions: Number of adverse reactions that occurred. When a single patient experienced multiple episodes of the same adverse reaction (PT), they should be counted as one event.

Types of adverse reactions: Should be calculated by SOC and by PT. Output data should be sorted in the order of international agreements and in the ascending PT code order. When a single patient experienced multiple episodes of the same adverse reaction (PT), they should be counted as one event.

Note: The version of MedDRA/J used should be provided.

